#### 7.1.7 Criteria for First Administration of Irinotecan

For Cycle 1 Day 3 irinotecan administration, the participant must have recovered well from any immediate post-operative effects **and** requires no more than 16 mg/day of dexamethasone. Otherwise the participant will be removed from treatment. Criteria found in 7.2.4 also apply.

#### 7.1.8 Dose Modifications

Table 7.2.4 details the criteria for disrupting treatment, dose modification and treatment discontinuation following an adverse event. See section 7.2.1 for general guidelines. The agent listed in Table 7.2.4 indicates the drug to which the toxicity is likely attributed based on previous trials to irinotecan and possible anticipated toxicities to the hCE1m6-NSCs. The investigator will determine attribution of all toxicities.

**Table 7.2.4 Criteria for Disrupting Treatment, Dose Modification or Discontinuation**

Adverse Event	Agent most likely attributed to toxicity	Treatment modification
Immune Response to NSCs (i.e. development of a new neurologic deficit not attributed to the location of brain tumor, fever without localizing source of infection, new or progressive rash, cough etc.)		
Grade 2 allergic reaction to the NSCs.  NOTE: a decision to stop study treatment will be based on development of clinical signs/symptoms of an immune response rather than a particular level of anti-NSC T cells or antibodies.	NSCs	
Hold study treatment.
 
Initiate immunological testing: Take 3-5 ml of blood in red top tube, kept upright at room temperature until delivery to CICSL. Store at 4 C after sample clots if unable to deliver sample the same day. Take additional samples (at least one additional sample) every two days.
 
Initiate supportive care: Restart dexamethasone to a dose of 4 mg twice daily; if patient is already taking dexamethasone, then increase dexamethasone to at least 4 mg twice daily.
 
Hold study treatment until sign/symptoms <math>\leq</math> grade 1, and resume treatment at the same dose, while continuing dexamethasone at a dose determined by the discretion of the treating investigator in consultation with the PI.

Grade 3 or 4 allergic reaction to NSCs  NOTE: a decision to stop study treatment will be based on development of clinical signs/symptoms of an immune response rather than a particular level of anti-NSC T cells or antibodies.		Hold study treatment.  Initiate immunological testing: Take 3-5 ml of blood in red top tube, kept upright at room temperature until delivery to CICSL. Store at 4 C after sample clots if unable to deliver sample the same day. Take additional samples (at least one additional sample) every two days.  Initiate supportive care: Restart dexamethasone to a dose of 4 mg twice daily; if patient is already taking dexamethasone, then increase dexamethasone to at least 4 mg twice daily. Continue dexamethasone until event resolves to $\leq$ Grade 1, and thereafter at a dose determined by treating investigator as clinically indicated.  If an immune response to the NSCs is considered at least possible, discontinue study treatment
Hematological Toxicities		
Thrombocytopenia Grade 1 ( $75 \times 10^9/L < LLN$ )	Irinotecan	Maintain treatment
Thrombocytopenia Grade 2 ( $50 - < 75 \times 10^9/L$ )		Maintain treatment
Thrombocytopenia Grade 3 ( $25 - < 50 \times 10^9/L$ )		Hold treatment until recovery to $\leq$ grade 2 (plts $\geq 50 \times 10^9/L$ ).
Thrombocytopenia Grade 4 ( $< 25 \times 10^9/L$ )		Hold treatment until recovery to $\leq$ grade 1 (plts $\geq 75 \times 10^9/L$ ). Resume treatment with an irinotecan dose reduction of 30 mg/m  .
Neutropenia (ANC) Grade 1 ( $1.5 \times 10^9/L < LLN$ )	Irinotecan	Maintain treatment
Neutropenia (ANC) Grade 2 ( $1.0 - < 1.5 \times 10^9/L$ )		Maintain treatment
Neutropenia (ANC) Grade 3 ( $0.5 - < 1.0 \times 10^9/L < LLN$ )		Hold treatment until recovery to $\leq$ grade 2 (ANC $\geq 1.0 \times 10^9/L$ ). First occurrence: Resume treatment with no dose modifications. Each occurrence thereafter: Resume treatment with an irinotecan dose reduction of 30 mg/m  .
Neutropenia (ANC) Grade 4 ( $< 0.5 \times 10^9/L < LLN$ )		Hold treatment until recovery to $\leq$ grade 2 (ANC $\geq 1.0 \times 10^9/L$ ). Resume treatment with an irinotecan dose reduction of 30 mg/m  .
Febrile neutropenia $\geq$ Grade 3 (ANC $< 1.0 \times 10^9/L$ , fever $> 38.5^\circ C$ )	Irinotecan	Hold treatment until recovery to $\leq$ grade 1 (ANC $\geq 1.5 \times 10^9/L$ ). Resume treatment with an irinotecan dose reduction of 30 mg/m  .
Serum Electrolytes		
Serum Electrolytes $\geq$ Grade 3 Calcium, Potassium, Magnesium, Phosphorous	Irinotecan (via diarrhea)	Provide supportive care per Section 6.7. Maintain treatment per investigator discretion.
Gastrointestinal		
Diarrhea Grade 1 (2-3 stools/day $>$ pretreatment)	Irinotecan	Maintain treatment
Diarrhea Grade 2 (4-6 stools/day $>$ pretreatment)		Hold both study drugs until resolved to $\leq$ grade 1, then resume treatment at pre-hold dose

Diarrhea Grade 3 (7-9 stools/day > pretreatment)	Irinotecan	Event present while on optimal anti-diarrheal therapy: Hold study treatment until the diarrhea decreases to $\leq$ grade 1, and then restart treatment with the dose of irinotecan reduced by 30 mg/m 
Diarrhea Grade 4 ( $\geq$ 10 stools/day > pretreatment)		Event present while on optimal anti-diarrheal therapy: Hold study treatment until the diarrhea decreases to $\leq$ grade 1, and then restart treatment with the dose of irinotecan reduced by 60 mg/m  .
Vomiting or Nausea Grade 1		Maintain treatment
Vomiting or Nausea Grade 2		Maintain treatment
Vomiting or Nausea Grade 3, despite maximal medical management		1st event present when on optimal anti-nausea therapy: Hold until resolved to $\leq$ grade 1, then resume treatment at pre-hold dose  <math>\geq</math> 2nd event present when on optimal anti-nausea therapy: Hold until resolved to $\leq$ grade 1, then resume with an irinotecan decrease of 30 mg/m  dose reduction
Vomiting Grade 4		Event present while on optimal antiemetic therapy: Hold study treatment until the vomiting decreases to $\leq$ grade 1, and then restart treatment with the dose of irinotecan reduced by 30 mg/m  .
Nervous System Disorders		
Grade 3 Nervous System Disorder that is not attributable to tumor location or neurosurgery and is considered a least possibly attributable to NSCs with or without irinotecan, and is not an immune response to study agents.	NSCs with or without irinotecan	Hold treatment until resolution to $\leq$ grade 1.  First event: If resolves within 7 days, resume treatment at pre-hold dose.  If does not resolve within 7 days, resume treatment with then dose reduce NSCs by 25% and dose reduce irinotecan* by 30 mg/m  .  Second event: Resume treatment with then dose reduce NSCs by 25% and dose reduce irinotecan* by 30 mg/m  .  *If the event occurred after recent administration with NSCs but before administration with irinotecan, dose reductions indicated only apply to NSCs. Otherwise both agents will be dose reduced.
Grade 4 Nervous System Disorder that is not attributable to tumor location or neurosurgery and is considered a least possibly attributable to NSCs with or without irinotecan, and is not an immune response to study agents.		Hold until $\leq$ grade 1, then perform brain MRI and PET/CT scans. If objective evidence of clinical benefit, continue tx* with dose reduce NSCs by 25% and dose reduce irinotecan by 30 mg/m  . If no objective evidence of clinical benefit, discontinue treatment.  *If the event occurred after recent administration with NSCs but before administration with irinotecan, dose reductions indicated only apply to NSCs. Otherwise both agents will be dose reduced.
Other unspecified Non-Hem Toxicities considered Related only to Irinotecan		
Grade 1	Irinotecan	Maintain treatment
Grade 2		Maintain treatment
Grade 3		Hold treatment until resolution to $\leq$ grade 1, then dose reduce irinotecan by 30 mg/m  .
Grade 4		Hold treatment until resolution to $\leq$ grade 1, then dose reduce irinotecan by 60 mg/m  .

Other unspecified Non-Hem Toxicities considered Related only to NSCs		
Grade 1	NSCs	Maintain treatment
Grade 2		Maintain treatment
Grade 3		Hold until $\leq$ grade 1, then dose reduce NSCs by 25% and dose reduce irinotecan by $30 \text{ mg/m}^2$ .
Grade 4		Hold until $\leq$ grade 1, then perform brain MRI and PET/CT scans. If objective evidence of clinical benefit, continue treatment with dose reduce NSCs by 25%. If no objective evidence of clinical benefit, discontinue treatment.
Other unspecified Non-Hem Toxicities considered Related to NSCs with irinotecan		
Grade 1	NSCs with irinotecan	Maintain treatment
Grade 2		Maintain treatment
Grade 3		Hold until $\leq$ grade 1, then dose reduce NSCs by 25% and dose reduce irinotecan by $30 \text{ mg/m}^2$ .
Grade 4		Hold until $\leq$ grade 1, then perform brain MRI and PET/CT scans. If objective evidence of clinical benefit, continue tx with dose reduce NSCs by 25% and dose reduce irinotecan by $30 \text{ mg/m}^2$ . If no objective evidence of clinical benefit, discontinue treatment.
Other unspecified Non-Hem Toxicities considered UNRELATED to study agents		
Other unspecified events of any grade considered unlikely to be related or not related to study agents.	UNRELATED	Maintain treatment with study agents. Interruption of study treatment is permitted if the investigator consults with the Principal Investigator to determine that this is in the best interest of the participant.

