**A DLT is defined as an adverse event that:**

- (a) is related to the administration of NSCs, irinotecan or the combination of NSCs with irinotecan, with an attribution of possible, probable, or definite, and
- (b) occurs during the first treatment cycle (including Cycle 2 Day 1 safety assessments), and
- (c) meets any of the following criteria:

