#### Nervous system disorders

5. Grade 3 CNS disorder lasting > 7 days that is not present at baseline and is not attributable to the location of the tumor or the neurosurgery.
6. Second occurrence of a grade 3 CNS disorder that is not present at baseline and is not attributable to the location of the tumor or the neurosurgery.
7. Any grade 4 CNS disorder that is not present at baseline and is not attributable to the location of the tumor or the neurosurgery.

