#### Non-hematological, non-nervous system toxicities

8. Grade 3 toxicity despite maximal medical therapy lasting > 7 days.

9. Grade 3 toxicity resulting in study agent discontinuation (permanently removed from study treatment).
10. Grade 4 toxicity, except grade 4 diarrhea that responds to maximal medical therapy within 3 days.

Please note: An allergic reaction to the NSCs is excluded from the DLT definition, because NSC dose reduction is not appropriate in this situation. The possible occurrence of allergic reactions to the NSCs is addressed by the study stopping rules (Section 5.6).

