#### **6.1.5 REQUIRED Increased Monitoring following Initial Indications of Possible Immune Response to the NSCs**

If a patient starts exhibiting signs/symptoms concerning for a possible immune response to the NSCs (such as development of a new neurologic deficit that cannot be attributed to the location of the patient's brain tumor, fever without a localizing source of infection, or rash not likely due to a concomitant medication), then **serum samples will be collected from the patient as soon as possible, and if feasible without putting the participant at increased risk, prior to administration of supportive care. A second sample, and additional samples if possible, should be taken approximately every 2 days to determine response to supportive care for the immune response.** The patient's stored serum samples from prior to start of study treatment, will also be analyzed for the same cytokine panel. See Section 8.6 for blood collection information.

In particular, we would be looking for changes in levels of IL-1RA, IL-6, IFN- $\gamma$ , IP-10, MIP-1 $\beta$ , MCP-1, IL-2RA, IL-8, IL-10, MIP-1 $\alpha$ , G-CSF, IL-15, IL-7, IL-2, TNF- $\alpha$ , IL-1 $\beta$ . Findings consistent with the presence of a "cytokine storm" would add strength to the conclusion that the patient is experiencing an immune reaction to the NSCs. See Section 12.2.5 for additional information regarding the cytokine panel.

A decision to stop study treatment will be based on development of clinical signs/symptoms of an immune response rather than a particular level of anti-NSC T cells or antibodies.

See Section 6.1.5 for required supportive care.

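### A qualifying new neurologic event in cycle 1 can be counted as a DLT or left out according to whether it is labelled an immune response to the NSCs, and the plan does not say which provision governs

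*Combined protocol and SAP*

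**What the plan says.** Section numbers follow the table of contents and the protocol's cross-references. The body prints some differently: 5.3.2 and 5.3.3 appear there as 5.1.2 and 5.1.3.

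- **Section 5.3.3, general conditions.** A DLT must be related to NSCs, irinotecan or both "with an attribution of possible, probable, or definite", and must occur in cycle 1, including the Cycle 2 Day 1 safety assessments.
- **Section 5.3.3, nervous system criteria 5 to 7.** These count a "Grade 3 CNS disorder lasting > 7 days that is not present at baseline", a second grade 3 occurrence, and "Any grade 4 CNS disorder that is not present at baseline and is not attributable to the location of the tumor or the neurosurgery". Each sets aside baseline conditions, tumor location and surgery. None sets aside an immune cause.
- **Section 5.3.3, closing note.** "An allergic reaction to the NSCs is excluded from the DLT definition, because NSC dose reduction is not appropriate in this situation". The note refers such reactions to the stopping rules.
- **Table 7.2.4, Immune Response to NSCs.** The signs given begin with "development of a new neurologic deficit not attributed to the location of brain tumor, fever without localizing source of infection". The only rows beneath are a grade 2 allergic reaction and a "Grade 3 or 4 allergic reaction to NSCs". In the second row, study treatment ends if an immune response is thought at least possible.
- **Section 6.1.5.** The signs that trigger serum sampling for a possible immune response include "development of a new neurologic deficit that cannot be attributed to the location" of the tumor.
- **Table 7.2.4, Nervous System Disorders.** These rows apply only if the event is at least possibly due to the NSCs "and is not an immune response to study agents".
- **Section 5.6.** Stopping rule ii needs two grade 4 allergic reactions rated probably or definitely related to the NSCs.

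**The concern.** DLT counts drive the 3+3 decisions, and through them the MTD or MFD on which the recommended phase II dose rests. A new neurologic disorder explained by neither tumor nor surgery is an obvious toxicity to look for when cells are given into the brain.

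For that kind of event the plan offers two routes. Under criteria 5 to 7 it counts. If it is regarded as an immune response, Table 7.2.4 grades it as an allergic reaction, and the note in Section 5.3.3 then takes it out of the DLT definition with no exception for neurologic events. The choice of route is not governed by any stated criterion. Section 6.1.5 says only that cytokine findings would strengthen the conclusion, and sets no threshold. Section 7.2.4 leaves attribution to the investigator, in an open-label study. At stake is whether the same clinical facts lead to escalation, to cohort expansion, or to a finding that the MTD has been exceeded.

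**Working it through.** **1. The plan's own figure.** Section 15 says six patients at the MTD/MFD detect a 0.25 toxicity rate in about 82% of trials. Check: 1 − 0.75^6 = 0.822. It reproduces and is not in dispute. The issue is which events enter the count.

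**2. The texts side by side.** Take a new grade 4 CNS disorder in cycle 1, possibly related to the NSCs and not due to tumor location or surgery.

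| Provision | Labelled a nervous system disorder | Labelled an immune response |
|---|---|---|
| Criterion 7, Section 5.3.3 | DLT | Met on its words (no immune exception) |
| Closing note, Section 5.3.3 | Does not apply | Excluded, if immune response means allergic reaction as in Table 7.2.4 |
| Discontinuation criterion, Section 5.3.3 | May also be met | Met on its words if treatment stops below 80%; its exception covers only baseline CNS toxicity due to tumor or surgery |
| Stopping rule ii, Section 5.6 | Does not apply | Not met: needs two grade 4 reactions, each rated probable or definite |

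A qualifying grade 3 event under the immune label likewise falls outside rule ii. The wording that separates the two categories in Table 7.2.4 governs dose modification and is absent from Section 5.3.3.

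**3. Effect of one label under Section 5.3.2.**
- 1/3 becomes 0/3: escalate instead of expanding the cohort.
- 2/3 becomes 1/3: expand instead of declaring the MTD exceeded.
- 2/6 becomes 1/6: escalate instead of declaring the MTD exceeded.

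**4. The denominator.** Section 5.3.2 requires at least 80% of the assigned NSCs and irinotecan, or a DLT, for a patient to be counted. At dose levels 2 to 4, cycle 1 has two administrations of each agent, so stopping before the second leaves 1/2 = 50%. Such a patient, if held not to have a DLT despite the discontinuation criterion, is not evaluable and is replaced. A patient whose event comes after both administrations can stay in as a non-DLT.

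**5. Illustration.** The documents give no rate, so p (true rate of qualifying events) and f (share labelled immune) are assumptions. Other DLTs are ignored.

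The chance of clearing a level at counted rate r is (1 − r)^3 + 3r(1 − r)^5. If relabelled patients stay in, r = p(1 − f). If they are replaced, r = p(1 − f)/(1 − pf).

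For p = 0.30:
- All count, r = 0.30: 0.343 + 0.151 = 0.494.
- f = 0.5, patients stay in, r = 0.15: 0.614 + 0.200 = 0.814.
- f = 0.5, patients replaced, r = 0.15/0.85 = 0.176: 0.559 + 0.201 = 0.759.

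| p | All count | Half relabelled, stay in | Half relabelled, replaced |
|---|---|---|---|
| 0.20 | 0.71 | 0.91 | 0.89 |
| 0.30 | 0.49 | 0.81 | 0.76 |
| 0.40 | 0.31 | 0.71 | 0.60 |

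The replaced column uses r = 0.10/0.90, 0.15/0.85 and 0.20/0.80.

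**The case against.** The best defence has four parts.

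First, Section 5.3.3 read alone is clear. Criteria 5 to 7 have no immune exception, and the closing note concerns allergic reactions, follows the list of non-nervous-system criteria, and never mentions immune responses. The conflict appears only when a Table 7.2.4 heading, written for dose modification, is brought in. This stands in part: the link is an inference. But the note speaks of the DLT definition as a whole, allergic reaction is defined nowhere else, and Table 7.2.4 is the only place where the plan grades an immune response.

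Second, the Table 7.2.4 rows are mutually exclusive. That is right, and a reader who infers that two rows apply to one event would be mistaken. What is missing is a test for choosing the row, and a rule for DLT counting.

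Third, the exclusion is deliberate, with a stated reason and a referral to the stopping rules. That also stands, so the documents do not support concluding that the neurologic criteria must prevail. It does not settle whether the exclusion was meant to reach them.

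Fourth, the protocol management team decides on escalation, all patients are followed for toxicity, and the recommended phase II dose also rests on the full toxicity profile. A relabelled event therefore remains visible. This limits the harm but leaves the 3+3 rule undefined for that event.

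**Conclusion.** The point holds as a conflict in the rule that sets the MTD. For a cycle 1 neurologic event that is at least possibly related and is grade 4, grade 3 for more than 7 days, or a second grade 3, the plan supports both counting and not counting. One label is enough to change a cohort decision. Under the assumptions shown, relabelling half the events at a 30% true rate raises the chance of clearing a level from 0.49 to 0.81, or to 0.76 with replacement. These figures show sensitivity and are not forecasts: Section 7.1.2 reports no grade 3 or 4 toxicity attributed to the NSCs in the first-in-human study of the parent line.

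Three stronger readings go beyond the documents.
- A reader might infer that every unexplained new deficit is affected. A grade 2 deficit, or a single grade 3 event resolving within 7 days, does not meet criteria 5 to 7.
- A reader might infer that escalation becomes certain. A clearance probability of 1.00 needs every event relabelled and no other DLT, and it ignores stopping rule ii and the discontinuation criterion.
- A reader might infer that the recommended dose will be too high. Relabelling can only raise the chance of clearing a level, but whether it would happen is unknown, and the final recommendation draws on more than the DLT count.

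**What to change.** Reconcile the DLT definition in Section 5.3.3 (discontinuation criterion, criteria 5 to 7 and closing note), Section 5.6, Section 6.1.5 and both blocks of Table 7.2.4, so that each qualifying neurologic event has one DLT status. Specifically:

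1. Define allergic reaction, for the purpose of the exclusion, separately from immune response.
2. State in Section 5.3.3 whether an event meeting criteria 5 to 7 is counted when an immune mechanism is suspected, and how the discontinuation criterion applies to it.
3. If it is not counted, state whether the patient stays in the denominator or is replaced, and how the event relates to the stopping rules.
4. State who assigns the label, on what basis, and that this is done before the escalation decision.

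Which provision prevails is for the sponsor to decide. The cost is a few sentences in Section 5.3.3 and matching terms in the other places. The small downside is that some events may change DLT status.

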### 5.1.2 Phase I Cohorts and Dose Escalation and De-escalation Criteria

Phase I Cohorts will be of 3 or 6 participants, as indicated by the dose-escalation criteria.

**Enrollment of the first 3 patients to a dose level will be staggered** by requiring that each of the first 3 patients be separately observed for 4 weeks (or until the DLT assessment period has ended) before the next patient can start treatment on that dose level.

Dose escalation will proceed through the identified doses without skipping any dose levels.

**To be counted for dose escalation**, a study patient must receive at least 80% of the assigned NSCs and 80% of the irinotecan for a particular dose level and be followed for 4 weeks OR have experienced a DLT as defined in Section 5.3.3.

All study patients enrolled are to be fully followed for toxicity; any study participant who is not evaluable for dose escalation will be replaced.

The NSC dose levels and irinotecan dose schedules are provided in Table 5.3.1. The first cohort will start at NSC dose level 1 and irinotecan schedule A.

The following dose escalation rules will be used, using the DLT definition as provided in Section 5.3.2:

- If 0/3 study participants experiences a DLT, the next cohort of 3 study patients will be treated at the next higher dose level.
- If 1/3 study participants experiences a DLT, the cohort will be expanded by another 3 study participants who will be treated at the same dose level for a total of 6 study participants.
- If 1/6 participants experiences a DLT, the next cohort of 3 study participants will be treated at the next higher dose level.
- If 2 or more participants of either a 3 participant or 6 participant cohort encounter a DLT, then the MTD has been exceeded. If applicable, three (more) participants will be enrolled at the next lower dose level.
- At least 6 patients will be treated at the MTD (or MFD, if the MTD is not reached).

If the 3+3 design rules indicate a need for de-escalation, the following will apply:

- If all DLTs in a dose level are attributed uniquely to irinotecan, then only the irinotecan schedule will de-escalate.
- If all DLTs in a dose level are attributed uniquely to NSCs, and are not attributed to 'NSCs with irinotecan', nor to irinotecan alone, then only the NSC dose level will de-escalate.

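### For toxicity attributed only to NSCs, Table 7.2.4 cuts irinotecan after a grade 3 event but not after a grade 4 event in patients who continue, and nothing explains why

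*Combined protocol and SAP*

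**What the plan says.** Table 7.2.4 has a block headed "Other unspecified Non-Hem Toxicities considered Related only to NSCs". Grades 1 and 2 call for no change. The other two rows are:

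- **Grade 3:** hold until the event is grade 1 or lower, "then dose reduce NSCs by 25% and dose reduce irinotecan by" 30 mg/m². Both agents are reduced.
- **Grade 4:** hold to the same threshold, then obtain brain MRI and PET/CT. If these show objective benefit, "continue treatment with dose reduce NSCs by 25%. If no objective evidence of clinical benefit, discontinue treatment". A patient who continues has NSCs reduced and no irinotecan change is stated; a patient without benefit stops.

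The neighboring blocks are split by attribution too. For toxicity related only to irinotecan, the grade 3 row says "then dose reduce irinotecan by 30 mg/m"² and leaves NSCs alone. For toxicity related to NSCs with irinotecan, the grade 3 row has the same wording as the NSC-only grade 3 row. The grade 4 row of that block, given benefit, says "continue tx with dose reduce NSCs by 25% and dose reduce irinotecan by" 30 mg/m².

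At cohort level, section 5.3.2 (Phase I Cohorts and Dose Escalation and De-escalation Criteria, which may print as 5.1.2) covers the case where the 3+3 rules call for de-escalation and every DLT is attributed uniquely to NSCs: "then only the NSC dose level will de-escalate".

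**The concern.** The block exists to separate NSC-only events from the rest, yet its grade 3 row treats them exactly as events attributed to the combination. Its grade 4 row does make the distinction. Followed as written, a patient who continues after a grade 3 event loses part of the irinotecan dose, and a patient who continues after a grade 4 event does not.

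The reduction is permanent. Item 4 of General Information, under Dose Modifications/Delays/Start of Cycle Criteria, bars re-escalation of either agent. The background section on irinotecan dose and schedule argues for the highest irinotecan dose possible, so an unexplained cut in that agent needs a stated reason. This is an operative rule that treating investigators would apply after serious toxicity, and they cannot tell from the text whether the difference is meant.

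**Working it through.** The plan states no figure to reproduce. The check compares rows and then sizes the disputed step. The grade 4 row's silence on irinotecan is read as no change.

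**1. Irinotecan cut (mg/m²) in every separate grade 3/grade 4 pair of Table 7.2.4**

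| Event | Grade 3 | Grade 4 |
|---|---|---|
| Thrombocytopenia | none | 30 |
| Neutropenia | none first time, 30 each later time | 30 |
| Diarrhea on optimal therapy | 30 | 60 |
| Vomiting on optimal therapy | none first time, 30 from the second | 30 |
| Nervous system | none if first event and resolved within 7 days, otherwise 30 | 30, if benefit |
| Other, irinotecan only | 30 | 60 |
| Other, NSCs with irinotecan | 30 | 30, if benefit |
| Other, NSCs only | 30 | none stated, if benefit |

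The nervous system rows also drop the irinotecan cut when the event comes after NSCs but before irinotecan. In seven of the eight pairs the irinotecan cut stays level or rises with grade. Only in the NSC-only pair does it fall.

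**2. Other rules that might explain it**

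From the same General Information list:
- Item 3 has both agents held together whatever the attribution. It governs holds, not reductions.
- Item 5 lets the investigator depart from the table with the Principal Investigator's written approval. That is a case-by-case exception.
- Item 6 covers events thought unlikely to be related to either agent, so it does not reach NSC-only events.

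**3. Size of the step**

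Cut as a share of dose = 30 / scheduled dose:
- Schedule A: 30/180 = 16.7%
- Schedule B: 30/150 = 20%
- Schedule C: 30/125 = 24%

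On schedule A, a patient who continues after grade 3 receives NSCs at 75% and irinotecan at 180 − 30 = 150 mg/m². A patient who continues after grade 4 with benefit receives NSCs at 75% and irinotecan at 180 mg/m².

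**4. Dose levels 1 and −1**

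Table 5.3.1 gives these patients a single NSC dose, on cycle 1 day 1, with irinotecan ongoing. The 25% NSC cut has nothing left to act on. The grade 3 row therefore cuts the only ongoing agent, while the grade 4 row changes no later dose for a patient who continues.

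**5. Reach into the cycle 1 data**

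Microdialysis and plasma sampling accompany only the cycle 1 day 3 irinotecan dose. A cut that starts at day 17 leaves these shares of cycle 1 irinotecan:
- A: (180 + 150)/360 = 91.7%
- B: (150 + 120)/300 = 90%
- C: (125 + 95)/250 = 88%

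All exceed the 80% that section 5.3.2 requires for a patient to count toward escalation. The exception is an event before the day 3 dose that has recovered in time for that dose to be given reduced. With both cycle 1 doses cut, the shares are 300/360 = 83.3%, 240/300 = 80% and 190/250 = 76%.

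**The case against.** The strongest reply is that the grade 4 row is not the milder one. It adds imaging and stops both agents for anyone without objective benefit, conditions that grade 3 lacks. That stands: the inversion is confined to grade 4 patients who continue.

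Three stronger readings are tempting, and the documents do not support them.

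- **That the two rows contradict each other, or contradict section 5.3.2.** The rows cover different grades, so no patient receives two incompatible instructions for one event. Section 5.3.2 sets the dose for further enrolment, whereas Table 7.2.4 sets a treated patient's own later doses, and both can be followed at once. The grade 4 row agrees with the cohort principle; only grade 3 departs from it.
- **That the cut lowers the SN-38 exposure under study.** Sampling is tied to the day 3 dose, so a later cut cannot affect it. Only an event before that dose could, and patients who have not recovered well from immediate post-operative effects are removed before irinotecan.
- **That it blurs attribution at the dose level.** A cut from day 17 leaves the patient evaluable on the 80% rule, and attribution is assigned to the event before the table is applied.

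It can also be said that the block is narrow. Immune reactions and nervous system events have their own rows, and the parent-line study saw no grade 3 or 4 toxicity attributed to NSCs. That limits how often the rule would be used, and the plan gives no expected frequency. Finally, reducing both agents may be deliberate, since the nervous system rows often do so. But those rows cover events attributed to NSCs with or without irinotecan and carry a timing exception that the NSC-only grade 3 row lacks. The documents do not show which cell is unintended.

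**Conclusion.** The inconsistency is real and unexplained. In the NSC-only block, grade 3 reduces both agents, whereas grade 4 with objective benefit reduces NSCs only. The grade 3 row does not fit its own heading and is out of line in principle with the cohort rule, without conflicting with it directly.

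The size is an irreversible irinotecan cut of 17% on schedule A, where the trial starts. The 20% and 24% figures apply only if the schedule has already moved to B or C. The effect is starkest at dose levels 1 and −1.

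The conclusion assumes that the grade 4 row's silence means irinotecan is unchanged, and it concerns only patients who continue. It is a wording problem in a dosing rule and should be corrected. It does not threaten the MTD determination or the planned SN-38 comparison.

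**What to change.** Reconcile the grade 3 and grade 4 rows of the NSC-only block with each other and with the block's attribution heading. If the difference is intended, state the rationale beside the table. The revised text should say explicitly what happens to irinotecan in each row, including for dose level 1 and −1 patients, who have no further NSC dose to reduce. This review takes no position on which modification is right.

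The cost is an edit to one or two table cells, or a sentence of explanation, in a protocol amendment. Sample size, visits and planned analyses are unchanged.
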